Participants: We will recruit 150 new clients (65+ years of age) referred for low vision rehabilitation to either of the two vision rehabilitation centres in Montreal (Lethbridge-Layton-Mackay and INLB, see partner letters of support), and 50 age-matched (by decade) older adults without visual impairment (to be recruited from spouses or family members of participants, as well as through open advertisement through media and senior groups). In addition, we have access to the *Banque des participants* of the *Centre de recherche institut universitaire de geriatrie de Montreal (CRIUGM; n > 1000)*. Within this database, it will be possible to match our control participants on variables such as age, gender, education, and other potential variables of interest such as MoCA score). Client-participants are

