The Low Vision Evaluation & Reading Intervention is delivered through rehabilitation services at the partner centers that are **regulated by the Quebec Ministry of Health**: Following Time 1 (within 3 months), participants will receive the full complement of services available and deemed suitable by their clinical staff and rehabilitation professionals of either rehabilitation centre. Both centres have a comparable service offer according to the provision of assistive devices and services regulated by the Quebec Health Insurance (RAMQ). These services are similar to those provided within the Blind Rehab Centers of the Veterans Affairs service offer in the USA^{36,37} and include but are not limited to: a full optometric exam to determine functional vision, including refraction and the prescription of appropriate near and distance glasses and optical devices. This is followed by an assessment by a low vision therapist and/or occupational therapist that will establish the client's functional priorities and rehabilitation goals. They provide hand-held optical magnification devices, electronic non-optical

magnification devices (e.g., portable or table-top closed-circuit TVs), or computer software for screen content magnification (e.g., ZoomText). All are provided free of cost for the client and with appropriate training and follow-up sessions in the home within 3 months, if required. Participants may undergo a systematic lighting assessment^{109,110} and may receive specific lighting recommendations that will improve their reading ability. In addition, clients will have access to referral services such as orientation & mobility training (for independent travel), registration for an adapted adult day centre for individuals with sensory loss¹¹¹, as well as the possibility to access psychosocial services, counsellors, social workers or other mental health professionals. The provision of assistive devices for magnification and reading is generally linked to a follow-up visit in the client's home 3 weeks after the initial rehabilitation appointment, in order to observe the use of the devices and strategies in the environment where the client lives. It is at this point that a decision is made with the client whether the devices are useful and will be assigned to the client as a permanent loan. Should additional needs emerge, the client is at liberty to contact the rehabilitation centre at any time to initiate a new service episode.

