Time 2 – 6-Months and Time 3 – 12-Months Follow-Up: Six and 12 months after the initial rehabilitation appointment, the research assistant will meet with each participant (at home or in the lab, according to their preference) in order to repeat the experimental protocol, and all reading, cognitive and hearing measures will be administered each time. Throughout the period of the protocol, data from the rehabilitation chart will be extracted as it becomes available, with the final data collection concluding after the 12-month follow-up.

Statistical Analysis – Functional measures: To analyze these data, we will examine change in cognitive test scores from baseline over time using mixed-effects regression models, adjusting for level of vision and hearing impairment as fixed or random effects, and compare across sensory group (VI/DSI/Control). The analyses will include consideration of potential moderators or confounders (i.e., gender, age, education). In addition, we will calculate effect sizes, confidence intervals and Bayes Factors for main effects, interactions, and all post-hoc analysis.

When reflecting on the question of a control group we further consulted with the rehabilitation centres and discussed recruitment approaches and limitations; however, for practical and ethical reasons we are not able to withhold rehabilitation services from a possible comparison group, and waiting times are too varied across the centers and seasons of the year to allow for a waiting-list control group. As a result, we are proposing a quasi-experimental repeated-measures design with the intent to let the participants act as their own comparison across time points.

In addition, the data allow us to follow potential **exploratory avenues of analysis:**

- 1) If the recruited participants naturally divide into individuals whose reading effort was reduced and their reading activity has increased, versus those where we do not observe a change in reading behaviour, we can compare these two groups directly (e.g., while still considering their hearing status, or their gender)

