inferior occipital gyrus, the middle occipital gyrus (and sulcus), the superior occipital gyrus, the cuneus, the lingual gyrus, the occipital pole, and the calcarine sulcus. CT will be investigated more specifically inside visual areas, namely V1 (BA17) – primary visual area, V2 (BA18) – secondary visual area, and V5/MT – visual area, middle temporal, by using an atlas from the Martinos Center for Biomedical Imaging (US) and the Institute of Neurosciences and Biophysics (Germany) (<http://surfer.nmr.mgh.harvard.edu/fswiki/BrodmannAreaMaps>). In order to examine if vision rehabilitation will result in changes in CT, we will examine by calculating percentage difference in extracted CT values for each of the above-mentioned visual regions pre- and post- reading rehabilitation. Differences between groups or between regions pre- and post-intervention will be considered significant at $p < 0.05$ after correction using false discovery rate.

Limitations & Mitigation Strategies:

Given the logistics of having the reading intervention delivered through services that are regulated by the Quebec Ministry of Health, we place our trust in the quality of rehabilitation service delivery without being able to control this aspect of the study; however, we believe that this trust is well deserved, given the quality and type of care provided in Quebec¹¹⁴⁻¹¹⁶. It is likely that a certain number of participants will self-select not to complete the 1-year follow-up or to abandon parts of the recommended intervention tools and techniques. Therefore, we will examine differences in participant characteristics and consider intent-to-treat within the statistical analyses. We expect certain variability in the cognitive status of our participants, as there are no cognitive exclusion criteria. This pragmatic approach to recruitment is chosen intentionally as we speculate that the beneficial effect of reading rehabilitation may become apparent at different levels of magnitude, depending on the cognitive starting point; however, this remains speculation at this point. Our statistical analyses will need to consider this additional source of variability.

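### The VI–DSI comparison pools patients from two centres with no centre term, so it is biased if the centres differ both in mean cognitive change and in VI/DSI mix

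*Combined protocol and SAP*

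**What the plan says.** Under Participants, the 150 patients are new clients "referred for low vision rehabilitation to either of the two vision rehabilitation centres in Montreal". Under Data Collection, the intervention is whatever is "deemed suitable by their clinical staff and rehabilitation professionals of either rehabilitation centre". The same paragraph says: "Both centres have a comparable service offer according to the provision of assistive devices and services". Under Limitations & Mitigation Strategies, the team writes: "we place our trust in the quality of rehabilitation service delivery without being able to control this aspect of the study".

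The model under Statistical Analysis – Functional measures is a mixed-effects regression of change in cognitive scores, "adjusting for level of vision and hearing impairment as fixed or random effects, and compare across sensory group (VI/DSI/Control", followed by: "The analyses will include consideration of potential moderators or confounders (i.e., gender, age, education". That section and the cortical-thickness section name centre nowhere, whether as a fixed effect, random effect, stratum or covariate. No section balances VI and DSI recruitment across the centres. The opening page makes VI versus DSI the second study question.

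**The concern.** VI and DSI patients are not randomised, and each is treated by one of two teams. A patient's centre could be related both to hearing group, if one centre sees relatively more dual-impaired clients, and to cognitive change, if services, staff, case mix or waiting differ. A variable linked to both is a confounder of the VI–DSI contrast. Letting participants act as their own comparison removes stable differences in level between centres, but not differences in change, and change is the outcome here.

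At stake is the answer to the second study question: a difference between centres could be read as a difference by hearing status.

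The documents contain one possible route. Time 1 precedes the first rehabilitation appointment, while the follow-ups are timed from that appointment. The plan notes that "waiting times are too varied across the centers and seasons of the year". The interval from baseline to follow-up can therefore differ by centre even if the services are identical.

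**Working it through.** **Plan's own figure.** Sample Size gives n = 141 for a 3×3 ANOVA at effect size 0.15, alpha 0.05 and power 0.95. For the group-by-time interaction, with a correlation of 0.5 between visits and sphericity (both assumed, since neither is stated), the noncentrality is 0.15² × 141 × 3 / (1 − 0.5) = 19.0 on 4 and (141 − 3) × 2 = 276 degrees of freedom. Power is 0.952, so the figure reproduces. Centre plays no part in it.

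**Inputs for the centre question**
- Patients at 12 months: 150 × 0.9 × 0.9 = 121.5, from the stated 10% attrition at each time point. An equal VI/DSI split is assumed, giving 60.75, or about 61 per group.
- SD of change: set to 1 (assumed).
- δ, the difference between centres in mean change: not in the documents; range 0.1 to 0.5 SD.
- g, the share of VI patients seen at centre A minus the share of DSI patients seen there: not in the documents; 0, 20 and 40 points. For example, 60% against 40% is a 20-point gap.

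**Bias.** With no true VI–DSI difference, mean change is μ + δπ(VI) in one group and μ + δπ(DSI) in the other, where π is the share at centre A. The contrast is therefore biased by δ × g. It is zero if either factor is zero.

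**False-positive rate without a centre term.** The variance of the contrast is v = [2 + δ²π(VI)(1 − π(VI)) + δ²π(DSI)(1 − π(DSI))] / 61. The two-sided rate is Φ(b/√v − 1.96) + Φ(−b/√v − 1.96), with b = δg. For δ = 0.3 and g = 0.4 (70% against 30%):
- b = 0.12
- v = (2 + 2 × 0.09 × 0.21) / 61 = 0.0334, so √v = 0.183
- rate = 10.1%

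| δ (SD) | g = 0 | g = 20 points: bias, rate | g = 40 points: bias, rate |
|---|---|---|---|
| 0.1 | 5.0% | 0.02, 5.1% | 0.04, 5.6% |
| 0.2 | 5.0% | 0.04, 5.6% | 0.08, 7.2% |
| 0.3 | 5.0% | 0.06, 6.2% | 0.12, 10.1% |
| 0.5 | 5.0% | 0.10, 8.4% | 0.20, 19.0% |

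Simulation (4,000 runs per setting) gives 6.0% and 10.6% for δ = 0.3, and 8.2% and 19.4% for δ = 0.5.

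**With a centre term on change.** In the same simulations the mean VI–DSI estimate is within 0.006 SD of zero, and the false-positive rate is 4.7% to 5.5%. The price is the correlation between group and centre: with equal groups and mirrored shares, the standard error rises by a factor of 1/√(1 − g²). That is 1/√0.96 = 1.02 at 20 points and 1/√0.84 = 1.09 at 40 points. The largest simulated ratio was 1.10.

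**The case against.** The strongest reply is that the harm needs two conditions, and the documents establish neither. They describe similar services under one provincial insurance scheme. DSI status is set by an audiometric threshold that the study measures itself, and nothing suggests that either centre supplies more DSI patients. A difference of 0.3 SD in cognitive change between two similar services would be large for an outcome on which, according to Sample Size, no effect-size estimate exists. All of this stands. It means that the bias may be negligible, not that the model protects against it.

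A second reply is that adjustment does not stop at gender, age and education. Vision and hearing level are in the model, chart data on services and devices are available for statistical control, and one objective is to identify further confounders. This also stands, and it would be wrong to say that demographics are the whole adjustment set. But none of these names centre. Vision and hearing level absorb only the part of a centre difference that runs through them.

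Third, the sentence on waiting times explains why a waiting-list control was ruled out. It is not evidence of different outcomes, and follow-up is aligned on the start of treatment. That is right: it shows a route, not an effect.

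A reader might also infer that the patient–control test has an inflated false-positive rate because variation between centres is ignored. That holds only if the two centres are treated as a random sample from a wider population of centres. The plan names two Montreal centres and makes no such claim, and a fixed centre term would not address it. It is a limit on generalisation, not an error in the model.

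**Conclusion.** The point holds as a conditional one and is a cheap improvement, not a serious flaw. The functional model lacks a centre term. If the centres differ in mean change by δ and in VI/DSI mix by g, the VI–DSI contrast is biased by δ × g. At 0.3 SD the false-positive rate is about 6% with a 20-point gap and about 11% with 40 points. At 0.2 SD or less with a 20-point gap, bias is at most 0.04 SD and the rate stays below 6%. With equal mix there is no inflation.

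These figures rest on an assumed change SD of 1, an equal VI/DSI split, and assumed values of δ and g. A reader might infer that the contrast is in fact biased; the documents do not support that.

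**What to change.** In the functional-measures model, add centre as a two-level fixed factor defined only among patients. Two levels are too few to estimate a random-effect variance.

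- If repeated scores are modelled, include centre-by-visit, because a centre main effect alone does not remove a centre difference in change. If change is the outcome, the main effect is enough.
- Estimate the VI–DSI difference in change within centre.
- Report the VI/DSI mix by centre.
- For patient–control contrasts, average over the two centres and state the coding. Coding patients +½ or −½ by centre and controls 0 does this.

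The pre-registered report promised under Study Design is a natural place to fix this before data are seen.

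The cost is at most three degrees of freedom (one for centre and two for centre-by-visit over three visits). The VI–DSI standard error rises by about 2% at a 20-point gap and up to about 10% at 40 points. Centre is already known for every patient, so no new data are needed, and the sample size does not change.

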Pilot data from our currently funded FRQS project focusing on cognition and AMD indicate correlations between sensory and cognitive variables in the expected directions insofar as individuals with faster reading speeds demonstrated better scores on the Montreal Cognitive Assessment^{57,58}. Given the information reviewed above, the logical direction for our investigation into the functional connection between LV and cognition is to examine the possible effects of reading rehabilitation on the cognitive abilities of LV patients over time. In order to dis-entangle the effects of visual and cognitive impairments in older adults, members of this research team have adapted cognitive tests so they can be administered to individuals with low vision^{59,60}. In parallel, we are also in the process of developing a vision-screening test that can be administered to individuals with various levels of cognitive impairment^{61,62}. This investigation will guide our future research efforts into the improvement of service provision in LV rehabilitation for the purpose of increasing the independence and health of older adults living with LV.

[figure not shown]
The objectives are to:

- Evaluate cognitive functioning and memory before, and 6 and 12 months after low vision reading rehabilitation using magnification in AMD patients, compared to those with dual (vision and hearing) impairments, and age-matched controls
- Correlate participant characteristics with all cognitive outcome variables in order to identify potential mediators, moderators or confounders

Hypotheses:

- Measures of reading effort (self-report and objective reading speed) will be statistically significantly reduced after participants have received strategies and tools to facilitate reading.
- Measures of reading behaviour will be negatively correlated with measures of reading effort (e.g., participants who report less effort will read a greater amount, more frequently and for longer)
- Individuals who demonstrate reduced reading effort and improved reading behaviour will demonstrate improved scores on cognitive tests after 6 months of having received rehabilitation strategies and tools, compared to those whose reading effort remains high or whose reading behaviour remains unchanged. These beneficial effects will be maintained after 12 months.
- Reading measures correlate with cortical thickness (CT) in the visual cortex;

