To subjectively assess reading effort, we will administer a reading habit questionnaire, a measure developed specifically to evaluate the extent and frequency to which an individual engages in reading activities during their activities of daily living, including reading for entertainment or education. This measure has previously been employed by our team³⁹ and includes questions on language background (e.g., mother tongue, language proficiency), assessed self-reported proficiency in reading (1=no ability, 5=fluent ability), and reading habits before and after onset of low vision (e.g., frequency, enjoyment, type of reading). In addition, participants will be asked to read English or French paragraphs from the

International Reading Speed Test (IReST)⁷⁷. It includes reading comprehension questions that have previously been developed and used in our lab in the context of a low vision reading evaluation using the iPad as a magnification device³⁹. They will also read the English or French version of the MNRead chart⁷⁸, a clinical assessment chart that allows for the measurement of reading acuity (smallest print read), reading speed (in words per minute), critical print size (smallest print at which reading speed is still optimal), and the Reading Accessibility Index⁷⁹, which considers reading ability over a range of print sizes. Finally, we administer a primed lexical decision task where the participant first reads a sentence (prime) and then decides on a word (target) as quickly and as accurately as possible. This task evaluates reading speed, vocabulary comprehension and ability to judge content congruency^{80,81}.

Measures of Participant Characteristics

Depression, Anxiety, Stress: Not surprisingly, the onset of age-related vision loss due to AMD is often accompanied with a multitude of emotional responses that can potentially interfere with the success of low vision rehabilitation. Therefore, the Depression, Anxiety and Stress Scale⁸² will be included in the protocol in order to identify individuals whose rehabilitation outcomes might be influenced by their psychological state. This 21-item questionnaire shows exquisite psychometric properties and has been validated in both English and French⁸³.

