- 2) If no such clear division occurs but participants naturally distribute along a continuum of reading effort and reading behaviour variables, we can simply use the reading measure(s) as co-variables to test whether any/all of the reading effort measures emerge as significant co-variables, and examine whether cognitive scores improved over time across our three groups, after removing the effect of reading rehabilitation success.
- 3) Finally, we will use **latent factor analysis** to explore whether specific clusters of variables are specifically associated with improvements in cognitive functioning and/or improved reading ability. This analysis will be led by [name], together with [name] and [name].

Statistical Analysis - Cortical thickness:

Regression analyses of visual impairment on cortical thickness will be investigated at each vertex of the cortical surface using general linear modeling. Cortical thickness will be modeled as a function of group by controlling for the effects of age, gender, and education. Resulting clusters will be considered significant at $p < 0.05$ using a Monte-Carlo simulation approach. Similar analyses will be performed for cortical volume and cortical surface area, with the addition of total intracranial volume as a nuisance factor¹¹². In addition, a region-of-interest approach will be used to extract the CT values in specific regions of interest using the Destrieux cortical atlas¹¹³ in FreeSurfer. More specifically, we will compare across groups CT values extracted within specific regions of the visual cortex including the

[name]

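### The graded analysis of reading change is planned only if patients do not divide into two groups; if they do, exploratory avenue 1 substitutes a two-group contrast that loses a modest amount of power for a graded effect (minor).

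*Combined protocol and SAP*

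**What the plan says.** After the main mixed-effects analysis, Statistical Analysis – Functional measures offers three further options, introduced by "In addition, the data allow us to follow potential exploratory avenues of analysis".

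- **Avenue 1** applies "If the recruited participants naturally divide into individuals whose reading effort was reduced and their reading activity has increased". The comparator and the test are then given as follows: "versus those where we do not observe a change in reading behaviour, we can compare these two groups directly". Hearing status or gender may still be considered.
- **Avenue 2** applies "If no such clear division occurs but participants naturally distribute along a continuum of reading effort and reading behaviour variables". In that case "we can simply use the reading measure(s) as co-variables to test whether any/all of the reading effort measures emerge as significant co-variables".
- **Avenue 3** is a latent factor analysis looking for clusters of variables associated with cognitive or reading improvement.

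The third hypothesis is worded as a group contrast: patients with less effort and better reading behaviour, "compared to those whose reading effort remains high or whose reading behaviour remains unchanged". The second hypothesis treats effort and behaviour as correlated quantities, expecting that "participants who report less effort will read a greater amount, more frequently and for longer". Reading Outcome Measures lists graded measures, among them "reading speed (in words per minute), critical print size (smallest print at which reading speed is still optimal), and the Reading Accessibility Index".

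The main model compares cognitive change across the three sensory groups, adjusted for level of vision and hearing impairment, with gender, age and education as possible moderators or confounders. Change in reading is not among its listed terms.

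**The concern.** The study's first question is whether better reading performance improves cognition. Since the main model lists no reading-change term, that link is examined in the exploratory avenues. Avenues 1 and 2 are written as alternatives, so the graded analysis is not planned when the patients look divided.

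A visible division does not make the graded scale redundant. Patients within each cluster still differ in how much their reading changed, and a two-group label ignores those differences. If the effect on cognition is graded, the contrast has less power and cannot show a dose-response relation. The plan also gives no cut-point and no criterion for a division. It does not say where discordant patients belong, for example those whose effort fell while their activity stayed the same.

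**Working it through.** **Inputs from the documents.** Participants: 150 patients. Sample Size: about 10% attrition per time point, alpha 0.05, r² = .20, and n = 141 for f = .15 at power .95. Patients remaining: 150 × 0.9 = 135 at 6 months; 135 × 0.9 = 121.5, taken as 121, at 12 months.

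**Assumptions, not in the documents.** The correlation r between reading change and cognitive change (0.15 to 0.30); cluster separation D in within-cluster SDs; cluster shares; patients only; a linear effect; a two-sided test.

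**1. The plan's own figure.** For the group × time interaction, λ = f²·N·m/(1 − ρ). With ρ = .5 and ε = 1 (software defaults, not stated in the plan), λ = 0.0225 × 141 × 3 / 0.5 = 19.0 on 4 and 276 df. Power is 95.2%, so n = 141 reproduces. It concerns the 3 × 3 design; the plan gives no power for the reading-to-cognition link.

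**2. Information kept by a split.** For two equal normal clusters cut at the midpoint, the correlation between the label and the graded score is

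k = [2φ(D/2) + (D/2)(2Φ(D/2) − 1)] / √(1 + D²/4),

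and the share of information kept is k². At D = 3: k = (0.259 + 1.5 × 0.866)/√3.25 = 0.865, so k² = 0.75.

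**3. Power.** Noncentral t with n − 2 df and δ = r√n/√(1 − r²). The split uses r·k in place of r. At r = 0.25, n = 121 and D = 3, δ falls from 2.84 to 2.43 and power from about 80% to about 68%.

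Power points lost, n = 121, equal clusters (graded power 38 / 61 / 80 / 93% at r = .15 / .20 / .25 / .30):

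| D | Kept | r = .15 | .20 | .25 | .30 |
|---|---|---|---|---|---|
| 2.5 | 71% | 10 | 14 | 15 | 11 |
| 3 | 75% | 8 | 12 | 13 | 10 |
| 4 | 81% | 6 | 9 | 9 | 6 |
| 5 | 86% | 4 | 6 | 6 | 4 |
| 6 | 90% | 3 | 5 | 5 | 3 |

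Clusters shared 30:70 raise the maximum to about 17 (D = 2.5, r = .25). With 135 patients, the same formulas give about 2 to 16.

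**4. Joint rule (effort down and activity up), simulated with 121 patients and r = .15 to .30.** Improvers against everyone else lose about 8 to 13 points at D = 3 and 5 to 7 at D = 4. With discordant patients left out, the losses are about 5 to 9 and 3 to 5.

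**5. At r = √.20 = .447.** Graded power exceeds 99.9%, and the loss is at most 0.8 points for D of 2.5 or more.

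**6. One-humped scores, for contrast (n = 121, r = .25).** Median split 20 points; joint rule about 28 to 30; 20:80 split 31.

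**7. If the effect is a pure step between clusters.** Correlation with true class, graded score against split: 0.71 v 0.68 at D = 2, 0.83 v 0.87 at D = 3, 0.89 v 0.95 at D = 4.

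**The case against.** The strongest reply is that avenue 1 is permissive, exploratory and conditional, and that it matches the third hypothesis, which is itself a contrast between improvers and others. All of that stands, and it is why the point is minor. It does not explain why the graded analysis should lapse when the condition is met.

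A second reply is that clear clusters are where a step effect is most plausible, and there the split is slightly more efficient once separation reaches about 3 SDs. This also stands. But the shape of the effect is unknown beforehand; a non-linear term can pick up a step, whereas a two-group label cannot recover a gradient.

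Third, the loss is negligible at the plan's r² of .20. That is correct arithmetic. However, Sample Size takes that value from vision-rehabilitation effects because none existed for cognition, so it does not estimate this link. The same section says the study can detect small effects, which makes smaller correlations reasonable to examine.

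Fourth, not every reading variable has a ready graded score. Words per minute and the Accessibility Index measure performance. Activity comes from the reading habit questionnaire, for which the plan describes a 1 to 5 proficiency rating and habit items but no total. This is fair: the graded model needs a stated activity score, as the two-group rule also does.

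**Conclusion.** The point holds as a minor one. Where patients visibly divide, the two-group contrast costs about 3 to 17 points of power, provided that the effect is graded, r is 0.15 to 0.30, and about 121 to 135 patients contribute. The loss is smallest when the clusters are far apart.

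Two stronger readings are tempting and are not supported:

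- A reader might infer losses of 20 to 30 points. Those belong to one-humped or very uneven splits, which the plan sends to avenue 2.
- A reader might infer that the study's main test is dichotomised, or that avenues 1 and 2 are the only routes to the reading question. The main analysis is the sensory-group mixed model, and avenue 3 also relates variables to cognitive and reading improvement.

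No size can be fixed from the documents, since they give no effect size for this link.

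**What to change.** Make the graded model unconditional. In the patient mixed model for cognitive change, enter change in reading effort and change in reading activity as continuous terms, with hearing status and gender, whether or not patients appear to divide. Name the score used for each. Report the slope with its confidence interval, and allow a spline or quadratic term in case the relation is curved or step-like. Keep the comparison of responders with unchanged patients, which mirrors the third hypothesis, as a secondary or descriptive display, and state its cut-points and where discordant patients go.

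The cost is a sentence or two of analysis wording, with no new data, visits or patients. Avenue 2 already accepts graded covariates, and the planned stage 1 pre-registered report is a natural place for the text. The downside is the slight loss of efficiency of the linear term if the truth is a pure step between clusters 3 or more SDs apart.
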